However, this evidence is weaker than generally assumed. There appear to be no studies of the anti-inflammatory effects of peanut consumption. Many studies of the effect of exercise on heart rate [38-40] or HRV [23, 41-43] report no effect or no difference between trained and sedentary participants and many that do show effects are cross-sectional comparisons of highly trained athletes with sedentary controls or longitudinal studies of training that have only a small number of participants [23, 44], lack a control group [45], or include only men [24, 26, 27, 46-49]. Thus, the data on the effect of exercise on inflammation must be regarded as promising but not fully established.

With regards to mitochondria, previous studies reveal that systemic inflammation involves mitochondrial signaling through several routes [57, 58]. A direct pathway by which this occurs is the leaking of mitochondrial circular DNA (mtDNA) in the systemic circulation in response to mitochondrial dysfunction, cellular damage or oxidative stress [57]. MtDNA are recognized as foreign or immunogenic and thereby trigger inflammation [59]. The indirect course involves the release of immunogenic molecules in the cell cytoplasm that induce proinflammatory gene response and the release of cytokines in various cells [59]. Finally, mtDNA encodes and modulates the electron transport chain whereby it ensures the proper detoxification of reactive oxygen species (ROS), and hence mitochondria can carry out its functions to produce energy and regulate major stress-response axes [60]. It follows that mitochondrial dysfunction may be directly associated with various pathologic states [60].

The potential pathophysiology of mitochondrial dysfunction requires a better understanding of the efficacy of various interventions in regulating mitochondrial function. Recent findings contend that vagus nerve activation and the release

of acetylcholine prevents inflammatory stimulation and mtDNA release [58]. Therefore, given the abovementioned studies linking nut consumption to reduced oxidative stress [16,17], and exercise to high vagal activity [27], we endeavor to examine the response of mitochondria to both interventions. Particularly, we will extract peripheral blood mononuclear cells (PBMCs) to examine mtDNA and mitochondrial enzymatic activity.

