Finally, with regards to the duration of exposure to both interventions, several studies of the effect of nut consumption on a variety of outcomes including inflammatory and autonomic show effects after 4 weeks. We modeled our intervention on those studies. Similarly, recent studies of high intensity interval training show effects on a variety of outcomes with as little as 2 weeks of training. Most use a 4-week program.

Selecting peanuts over other nuts was a compromise taking into consideration several factors. The best evidence for anti-inflammatory effects of nuts is in interventional studies of pistachio nuts. For example, West et al. [19] and Sauder et al. [20] found lipid lowering, anti-hypertensive, and anti-inflammatory effects of 4 weeks of consumption of pistachio nuts. The best evidence on peanut consumption comes from an observational study by Bao et al. [14] who showed substantial effects on mortality from diets heavy in a variety of nuts including peanuts. Thus, although the evidence of an anti-inflammatory effect of nuts is stronger for pistachios, peanuts are much cheaper and since the overall premise of this study is to test a public health intervention, we decide to test peanuts in this pilot grant.

This application is based on the discrepancy between consensus recommendations and the reality of health behavior change, and is informed by the opportunity to exploit what appears to be a common pathway by which nut consumption and exercise may exert their cardioprotective effects: the cholinergic anti-inflammatory reflex {Tracey, 2002 #6544}. Through this reflex, acetylcholine released by the vagus nerve effectively inhibits cytokine production in the principal organs of the innate immune system, the reticuloendothelial system in the spleen and the liver [50, 51].

Specific Aims and Hypotheses

Concisely state the objectives of the study and the hypothesis or primary research question(s) being examined. There should be one hypothesis for every major study procedure or intervention. For pilot studies, it is important not to overstate the study's objectives. If there are no study hypotheses, describe broad study goals/aims.

Hypothesis/Objectives

We propose to conduct an innovative pilot crossover non-inferiority trial to collect preliminary data with the aim, ultimately, of testing the hypothesis that the anti-inflammatory effect of peanut consumption is at least as great as that of short term (four week) high-intensity aerobic exercise.

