Our aims are to test the hypotheses that:

1. Plasma levels of IL-6 and TNF- α are reduced by peanut consumption and that this effect is at least as great as the effect of high-intensity aerobic exercise.
2. Consistent with the cholinergic anti-inflammatory hypothesis, peanut consumption and high intensity exercise will be associated with an increase in heart rate variability.
3. Mitochondrial enzymatic activity is altered in response to both interventions: exercise and peanut consumption

Inclusion/Exclusion Criteria

This section details your study sample(s) and addresses the requirement for risk minimization.

You may choose to divide your sample by population (healthy controls vs. subjects) or by procedure (subjects who will have an MRI) and then define different sets of criteria for each.

For each sample, create or insert a table to describe detailed criteria for study inclusion and exclusion and the method you will use to ascertain each criterion. The method of ascertainment may describe tests, scales and instruments. When relevant, indicate the level of training of the person who will make the assessment (e.g. clinical interview by a psychiatrist).

Inclusion/Exclusion Criteria needs to be numbered and listed in outline form (see Table template below).

INCLUSION CRITERIA	METHOD OF ASCERTAINMENT
Of either sex, age 21–45 years English-speaker	Telephone screen
Overweight or obese	BMI 27.0 – 34.9 kg/m ²
Sedentary	Baecke Physical Activity Questionnaire of <10
Home computer access	Participant disclosure

[figure not shown]
EXCLUSION CRITERIA	METHOD OF ASCERTAINMENT
1. Cardiovascular disease	Medical History Interview
2. Uncontrolled high blood pressure (blood pressure \geq 140/90). Individuals with controlled hypertension (i.e. under medical treatment) and blood pressure lower than 140/90 will not be excluded.	Measurement taken at consent before eligibility is determined
3. Current or recent (evidence of disease x 5 years) non-skin neoplastic disease or melanoma. Prostatic carcinoma will not be grounds for exclusion.	
4. Active hepatic disease (not a history of hepatitis) or primary renal disease requiring dialysis, primary untreated endocrine diseases, e.g., Cushing's disease or primary hypothalamic failure or insulin dependent diabetes (Type I or II).	Medical History Interview
5. HIV infection	
6. Pregnant or lactating (participation allowed 3 months after ceasing lactation).	

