Qualifying participants will undergo a two-week run-in period, first of control snack consumption and then stretching to screen for adherence. They will then undergo a submaximal cardiopulmonary exercise test, sCPET 1, to establish baseline $VO_{2\max}$ and confirm eligibility as a sedentary individual. They will then proceed to Lab Session 1.

Women will be asked to wait until they are in the post-ovulatory mid-luteal phase of their menstrual cycle (as indicated by a home ovulation kit) to schedule the first sCPET, such that all their later sCPET and laboratory tests will similarly align with the mid-luteal phase.

Women participants receive a 7-day ovulation home kit at the start of the study to estimate the ovulation date. The kit contains strips on which participants are asked to urinate every day following the end of their menstrual period until ovulation is detected – measured by a surge in luteinizing hormone (LH), also known as the onset of the luteal phase. All study tests are scheduled for this period within the menstrual cycle.

Participants will then be randomized to either 4 weeks of high intensity interval aerobic exercise or peanut consumption (2 times a day). Participants starting with peanuts will meet with the research assistant/dietitian who will assess their eating patterns by implementing a 24 hour recall. Dietary information will be used to help guide the subjects in maintaining an isocaloric diet during the protocol. Additionally, the Mifflin St. Jeor calculation will be used to determine the daily number of calories needed for each subject in order to maintain their weight.

All adherent and qualifying subjects go on to Laboratory Session 1 (anthropomorphic indices, HRV, fasting blood drawn). Participants starting with the exercise intervention will be instructed on how to use the exercise facility, and participants starting with peanuts will be given peanuts and instructed on food substitution in order to maintain an isocaloric diet. All contact with participants about group assignment, test scheduling, adherence monitoring, etc. is conducted by trained research assistant “coaches.”

After the first 4-week intervention (exercise or peanuts) all participants will undergo Laboratory Session 2 and sCPET 2, and proceed to a 4-week washout period.

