quantities (>1 serving/day) during the study but can otherwise maintain their current diet. Participants are assessed for alcohol, caffeine, and cocoa consumption and must maintain their levels of intake of throughout the study.

Laboratory Testing Sessions

Participants abstain from any physical exercise for a 24-hour period prior to each testing session to control for acute effects of exercise on inflammatory markers. Participants arrive for Laboratory Sessions in the morning after an overnight fast. 45 ml (9 teaspoons) of venous blood will be drawn for cytokine, PBMCs and hormone analysis. For women, laboratory sessions are scheduled in the mid-luteal phase of the menstrual cycle, to control for cycle effects on Heart Rate Variability [54]. After the blood draw, they receive a light breakfast providing 15% daily energy intake as established during the dietary assessment. Waist circumference is measured with a Gulick anthropometric tape. Height is measured using the Seca 214 Portable Height Rod (Seca Corp., Hamburg, Germany). Weight and body composition are measured using a Tanita BF-350 monitor (Tanita UK Ltd., Middlesex, UK).

Participants then are instrumented with ECG leads and respiration monitoring bands and rest quietly in the supine position for 5 min, after which 20 min of resting ECG and respiration data are collected. These data are collected in all Laboratory Sessions.

Treatment Conditions

In this crossover design, participants are randomly assigned to either the peanut condition followed by aerobic exercise or aerobic exercise followed by the peanut condition. Following the guidelines for non-inferiority trials, the exercise intervention, as the more widely accepted anti-inflammatory treatment, functions as the comparison for the peanut intervention.

Peanut Diet

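### Aim 1 sets out to test now that peanuts work at least as well as exercise, but the protocol calls the exercise effect not fully established and randomises no untreated condition; restate it as estimation.

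*Protocol*

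**What the plan says.** Specific Aims and Hypotheses introduces the numbered aims with "Our aims are to test the hypotheses that". Aim 1 is that plasma IL-6 and TNF-alpha "are reduced by peanut consumption and that this effect is at least as great as the effect of high-intensity aerobic exercise". It has two halves: a reduction on peanuts, and a comparison with exercise.

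Treatment Conditions invokes the guidelines for non-inferiority trials and says that "the exercise intervention, as the more widely accepted anti-inflammatory treatment, functions as the comparison for the peanut intervention". The same section randomises participants only to the order of the two interventions. The two-week run-in is the same for everyone. After the first intervention "all participants will undergo Laboratory Session 2 and sCPET 2, and proceed to a 4-week washout period", also common to all.

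On prior evidence, Background, Significance, and Rationale concludes that "the data on the effect of exercise on inflammation must be regarded as promising but not fully established", and says of peanuts: "There appear to be no studies of the anti-inflammatory effects of peanut consumption".

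The Hypothesis/Objectives paragraph just above the aims describes a "pilot crossover non-inferiority trial to collect preliminary data with the aim, ultimately, of testing the hypothesis". The form's own instruction at the head of that section begins "For pilot studies, it is important not to overstate".

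**The concern.** A non-inferiority result takes its meaning from a comparator known to work under the trial's conditions. If that is uncertain, similar results on peanuts and exercise may mean that both reduce inflammation or that neither does. The protocol itself records the uncertainty, and no randomised untreated condition is there to resolve it.

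The reduction half of Aim 1 is meant to exclude the case of two null effects. It is a change from before to after within one condition, with nothing concurrent to set it against. A non-specific fall in the markers over time could satisfy it, and such a fall largely cancels out of the peanut-exercise comparison, so the comparison would not expose it.

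At stake is the pilot's conclusion. As worded, a before-after fall plus a small difference would answer Aim 1 in the affirmative: peanuts are anti-inflammatory, and not inferior to exercise. The design cannot carry that claim. The objectives paragraph, which defers the test, does not ask for it, so the two passages conflict.

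**Working it through.** **Inputs.** From the protocol: 20 completers of 30 enrolled (Description of Subject Population), two sequences, and laboratory sessions before and after each intervention. The protocol gives no margin, SD, significance level or decision rule, so there is no stated figure to reproduce. Assumed for illustration: 10 completers per sequence, one-sided 0.025, both interventions inert, margins of 0 to 0.8 SD of the paired peanut-minus-exercise difference, and a correlation of 0 to 0.5 between the two periods' changes.

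**Step 1. Comparative half alone, one marker.** With 20 completers and 18 degrees of freedom, the pass probability at a true difference of zero is P(T > t(0.975, 18)), where T is noncentral t with noncentrality margin × √20. At 0.5 SD, for example, the noncentrality is 0.5 × 4.472 = 2.236.

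| Margin (SD of paired difference) | Passes when neither intervention works |
|---|---|
| 0 | 2.5% |
| 0.2 | 13% |
| 0.3 | 25% |
| 0.4 | 40% |
| 0.5 | 56% |
| 0.8 | 92% |

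Passing at a generous margin says nothing about whether either intervention works. Read literally, with a zero margin, the claim passes only at the nominal rate.

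**Step 2. Both halves, one marker, nothing else changing.** The reduction half alone passes in 2.5% of trials, which caps the joint rate. In simulation (60,000 trials per setting) it stays at or below about 2.5% at every margin.

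**Step 3. Both halves, one marker, with a non-specific fall.** The fall is in SD of the within-period change. If it occurs in both periods, it cancels within each participant's difference. If it occurs in period 1 only, it cancels between the two sequences, and the mean fall on peanuts is halved because half the participants take peanuts in period 2 (0.3/2 = 0.15 SD; 0.5/2 = 0.25 SD). Simulated joint pass rates, low end at margin 0 and high end at 0.8 SD:

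| Fall | Period 1 only | Both periods |
|---|---|---|
| 0.3 SD | about 1–9% | about 2–25% |
| 0.5 SD | about 1–18% | about 2–56% |

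The both-period ceilings are the rates for the reduction half alone: 25% and 56% by noncentral t with noncentrality 0.3 × √20 = 1.34 and 0.5 × √20 = 2.24. If IL-6 and TNF-alpha must both pass, rates are lower: at margins of 0.5–0.8 SD and marker correlation 0–0.5, 0.1–0.4% with no fall, and 4–11% or 15–39% with a both-period fall of 0.3 or 0.5 SD.

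**Step 4. What the design can deliver.** The 95% confidence half-width for the peanut-minus-exercise difference is t(0.975, 18)/√20 = 2.101/4.472 = 0.47 SD of the paired difference. The washout change has the same half-width in its own SD, and 2.262/√10 = 0.72 SD within one sequence of 10. A washout drift of 0.3 or 0.5 SD would be detected only 25% or 56% of the time (two-sided 0.05), so that check can only be descriptive.

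**The case against.** **It is already called a pilot.** The objectives paragraph says so, the aims sit directly beneath it, and no decision rule or planned claim of efficacy is stated. The sentence about overstatement is the form's template text, not the investigators' commitment. That reduces the conflict to one of wording, but does not remove it: the list still says that the hypotheses are to be tested, and Treatment Conditions still invokes non-inferiority.

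**The large percentages depend on assumptions.** This stands. Small margins give small rates, and regression to the mean or habituation would act mainly in period 1, where the rates are much lower. The protocol also limits drift: a run-in before baseline, stable weight and activity, diet restrictions, fasting draws, mid-luteal timing in women, and no selection on these markers. A reader might infer from Step 3 that the trial has an inflated false-positive rate. The documents do not support that, because they give no evidence that a fall occurs.

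**Exercise is a reasonable comparator.** A reader might infer that its effect has no support. That goes too far: the Background cites studies reporting anti-inflammatory effects and calls the evidence promising, and the criticisms just before that judgement mostly concern heart rate and its variability. Being more widely accepted than peanuts is compatible with this. The point needs only that the effect is uncertain, which the protocol says.

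**The washout serves as a control.** It is untreated, with laboratory sessions at both ends, but it is not randomised, may contain carryover, and is imprecise at this size.

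**Leave it to the analysis plan.** A margin and the reporting details could go there. A concurrent control, or an established comparator effect, could not.

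**Conclusion.** The point holds as one about what the trial may conclude. By the protocol's own account the comparator's effect is not fully established, and neither intervention has a concurrent control, so Aim 1 as worded asks for a conclusion that the design cannot support. It also conflicts with the objectives paragraph. This follows from the text and does not depend on any assumed figure.

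The size is illustrative. With inert interventions, the comparison alone passes in 2.5–92% of trials over margins of 0–0.8 SD, while Aim 1 as a whole stays at or below about 2.5% for one marker unless something non-specific lowers the markers. No stated figure in the protocol is shown to be wrong. Nor is the crossover unsound: it gives a valid randomised estimate of the peanut-minus-exercise difference, subject to carryover. The change is worth making because it is cheap and alters the permitted conclusion.

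**What to change.** - In Specific Aims and Hypotheses, bring Aim 1 into line with the objectives paragraph: estimate the peanut-minus-exercise difference in change of IL-6 and TNF-alpha, with a 95% confidence interval, and report the within-person SD for planning the later trial.
- In Treatment Conditions, describe exercise as the reference condition for that estimate.
- State that neither intervention has a concurrent control, that each condition's before-after change is therefore uncontrolled, and that the pilot will draw no confirmatory non-inferiority or efficacy conclusion.
- Optionally, report the change over the washout by sequence as a descriptive check: a continued fall would suggest drift, and a reversal would suggest rebound after the intervention.

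The cost is wording and reporting. The data are already collected at the four laboratory sessions, and the number of participants need not change. The downside is a more modest claim: the pilot yields an estimate and an SD, not a verdict. The rewording does not show that either intervention works; it removes a conclusion that the design cannot support.

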7. Medications that alter inflammation or autonomic nervous system activity.	
8. Any history of psychosis or ECT	

9. Psychotic disorder (lifetime)			
10. Current or recent (past 5 years) Major Depressive Disorder, Bipolar Disorder, or Anxiety disorder			
11. Current or recent (within past 12 months) alcohol or substance abuse or dependence. Recent use (past month) of recreational drugs.	Medical History Interview		
12. Probiotic and dietary supplements that affect inflammation or the ANS			
13. Physically active	CPET1	VO _{2max} (ml/kg/min)	VO _{2max} (ml/kg/min)
	Age (yrs)	Male	Female
	21-29	>41.0	>35.2
	30-39	>39.5	>33.8
	40-49	>37.6	>32.3
14. Peanut allergy in subject or in family of subject. Subjects who are unsure of their allergy status will be excluded.	Diet Interview		
15. Hormonal Birth Control	Telephone Screen		

Study Procedures

Provide a clear, concise narrative of study procedures with special attention to the subjects' involvement. Detail the overall study timeline and location of study procedures, list all interventions, assessments and interviews, estimate the duration of each procedure, provide dosing schedules, identify study personnel involved in each procedure, and provide credentials for relevant personnel. For complicated study designs, we strongly encourage attaching tables, flow-charts, and study algorithms.

Sedentary, overweight or obese but otherwise healthy 21-45 year old participants from Columbia University Medical Center/New York Presbyterian Hospital, and surrounding community, will be recruited through posted flyers **and the Columbia RecruitMe online platform**. After screening and eligibility determination through physical activity assessment and medical history interview they will provide informed consent. Participants must agree to maintain constant body weight(<±3%) and current levels of physical activity, except for the study interventions, throughout the protocol. They must also agree to abstain from omega-3 fatty acids supplements, high fat fish consumption (>8oz/week), and nuts (besides the peanuts given). Additionally, high quantities (>1 serving/day) of flax seeds, chia seeds, soy, canola, including oils, or food products that contain these ingredients in high quantities must be avoided, but subjects can otherwise maintain their current diet. The experimental protocol is presented in the Flowchart.

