By the end of the washout period, all participants will undergo sCPET 3. Participants who cross-over to the dietary peanut intervention will meet with the research assistant/dietitian to assess their eating patterns to inform instructions on maintaining an isocaloric diet during the protocol. Participants who cross-over to the exercise intervention will be instructed on how to use the exercise facility. All participants will return for Laboratory Session, and participants who will be consuming peanuts will be given peanuts and instructed on food substitution in order to maintain an isocaloric diet.

Following the second 4-week intervention, all participants return for follow-up Laboratory Session 4 and sCPET 4. All outcome variables (VO_{2max}, HRV, inflammation, and PBMC's) and control variables (weight, body composition and diet quality and physical activity independent of training) will be collected at 4 time periods in the study. All contact with participants about group assignment, test scheduling, adherence monitoring, etc. is conducted by trained research assistant “coaches.”

Two-Week Run-in Period

In previous projects, the run-in period has allowed us to identify participants likely to adhere to the protocol and thus has substantially reduced dropout.

For the first week, participants will eat a run-in snack, commercially available pita chips, twice a day as between meal snacks. Research assistants will collect the numbered pita packets at the end of the week to check for compliance. Only participants who consume at least 11 out of the 14 pita snacks and maintain weight will continue to the second week of the run-in.

For the next week, participants will be instructed on how to perform the stretching phase of the run-in and how to use the Polar Heart Rate (HR) monitor. Participants will complete 4X/week for 30 min of stretching at home while wearing the Polar HR monitor. Coaches will provide detailed instructions on how to complete the stretching.

Stretches consist of arm circles, neck rotations, toe reach, gluteal stretches, lateral leg swings, achilles stretch and ankle rolls. Adherence will be monitored using gym attendance records and HR monitor data. Only participants who perform at least 3 out of the 4 stretching sessions can continue on to the sCPET, Lab Session 1, and randomization.

Submaximal Cardiopulmonary Exercise Test

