Regular daily caloric intake of each subject will be estimated using data from 24hr recalls, the Miflin-St. Jeor equation, and stress/activity factors. Participants will consume dry roasted, unsalted peanuts equivalent to approximately 10% of daily energy intake twice a day (total=20% total daily energy intake), which will range from approximately 400kcal to 600 kcal, which corresponds to about 2.4 ounces to 3.6 ounces. Peanuts will replace protein and fat containing foods so that the daily caloric intake will not differ from participants' typical diet. Nutrient content will be analyzed by Covance Laboratory (Madison WI). To assess compliance, participants will be asked to bring back the empty, numbered peanut packets by the end of every week and will be given new packets weekly. Additionally, subjects will be informed that they will be randomly assessed weekly for compliance; they will be asked to provide details of when and where they consumed their packets the previous day. Research assistants will provide guidance on how to maintain compliance.

High Intensity Interval Training (HIIT):

Based on previous studies [55], participants will engage in 4 training sessions per week over a 4-week period, with 24 hour rest-periods between each training day. Participants will have the option to exercise either at the PlusOne Fitness Center at CUMC/NYPH, or at home on a Sunny Folding Climbing Stepper (Sunny Health & Fitness, Los Angeles) which will be delivered to the participant via UPS or FedEx, and be retrieved by Behavioral Medicine staff at the end of the study,

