at no cost to them. Participants will indicate which exercise modality they choose at the informed consent appointment, and those who elect to do the home-based program will have the Sunny Stepper delivered to their home after the 2-week run-in period is completed. Each session begins with a 3 min low intensity warm-up, and then participants exercise as rapidly as they can for 20 seconds, aiming to reach 85% of their maximum heart rate as established during the submaximal cardiopulmonary exercise testing (sCPET) (see Sec D.3.4.). This 20 second period is followed by 40 seconds of low intensity exercise. Participants complete 8 such intervals for sessions 1 and 2, 10 intervals for sessions 3 and 4, and 12 intervals thereafter. A brief training program similar to this yielded a 9% increase in VO₂max in only 12 days. High Intensity Interval Training (HIIT) also has been shown to be safe. In over 175,000 hours of cardiac rehabilitation, the cardiovascular event rate was extremely low [56].

Criteria for Early Discontinuation

Define criteria that will be used to exit or drop subjects from the study. Indicate the time points when such criteria will be applied, and describe the rating instruments, parameters, and thresholds that will lead to a decision to terminate a subject's participation. In addition, explain procedures for managing subjects who are dropped from the protocol.

For treatment studies: To minimize risks to subjects, operationalized drop-out criteria should be defined so that subjects who worsen, or in some cases, fail to improve, are removed from the study and offered standard care. The threshold for drop-out should consider the level of risk associated with non-improvement for the specific disorder, the availability of alternatives, and the typical required duration of treatment. For example, emergence of suicidal intent, or psychosis, should prompt immediate clinical evaluation and withdrawal from the study.

Subjects will be dropped from the study at any point during the entire study in the event of serious illness or injury, or if they develop an allergy to peanuts or at any point during the exercise phase if an injury occurs. All participants will have been carefully screened prior to the initiation of the exercise protocol to minimize the risk of adverse events.

Participants will be required to present a note from a physician indicating medical clearance for exercise training.

Blood and other Biological Samples

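### The home stepper is collected only when the study ends, so exercise-first home users keep the comparator's equipment through the washout and the peanut period: an avoidable route of contamination, not a shown bias

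*Protocol*

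**What the plan says.** The Protocol's section High Intensity Interval Training (HIIT) lets participants train at a fitness centre or at home on a stepper, and they choose at the consent appointment. The home device will "be retrieved by Behavioral Medicine staff at the end of the study". On delivery the same section says that "those who elect to do the home-based program will have the Sunny Stepper delivered to their home after the 2-week run-in period is completed". Neither sentence distinguishes the two sequences.

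Study Procedures gives the timeline. After the first 4-week intervention participants "proceed to a 4-week washout period", and a second 4-week intervention follows. "By the end of the washout period, all participants will undergo sCPET 3", and the next laboratory session (the third by order) comes before the second intervention. Around that time, "Participants who cross-over to the exercise intervention will be instructed on how to use the exercise facility".

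Two safeguards are written in. Participants must agree to maintain "current levels of physical activity, except for the study interventions, throughout the protocol". The control variables, including "physical activity independent of training) will be collected at 4 time periods in the study", are collected alongside the outcomes, among them VO2max.

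**The concern.** The exercise period is the comparator in this crossover non-inferiority design (Treatment Conditions). The washout exists so that the effect of the first intervention can fade before the second baseline. A participant who has finished the exercise period but still has the training device at home can continue training in the washout or in the peanut weeks.

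The HIIT section itself reports a fast response: "A brief training program similar to this yielded a 9% increase in" VO2max in 12 days. A 4-week window is therefore long enough, in principle, for continued use to matter. Use in the peanut weeks would add an exercise effect to the peanut change and make the two conditions look more alike, which favours non-inferiority. Use in the washout would disturb the baseline of the second period.

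The Peanut Diet section controls supply of the other intervention week by week, with numbered packets issued and returned. The stepper has no comparable tie to its own period.

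**Working it through.** **Time with the device.** The plan states no figure for this, so there is none to reproduce. The inputs are the period lengths in Study Procedures and the delivery and retrieval rules in the HIIT section.

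- Weeks after the run-in: 4 + 4 + 4 = 12.
- Exercise-first home user: exercise in weeks 1–4, washout in weeks 5–8, peanuts in weeks 9–12, retrieval at the end. Weeks held outside assigned exercise: 4 + 4 = 8, and 8/12 = 67%.
- Peanut-first home user: peanuts in weeks 1–4, washout in weeks 5–8, exercise in weeks 9–12. The delivery rule gives only an earliest date. Delivery straight after the run-in gives 4 + 4 = 8 weeks held early. Delivery just before the exercise period gives 0. The range is 0 to 8.
- These are nominal weeks. If the end of the study means the end of the whole trial and not of the participant's own follow-up, the exercise-first figure is a minimum.

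**Direction of an effect, if there were any use.** Let P and E be the true benefits of peanuts and exercise over 4 weeks, and f the fraction of E that off-schedule use produces. Let a = 1 if the stepper is used in the peanut weeks and w = 1 if it is used in the washout (0 otherwise). Assume that the effect is a level reached within 4 weeks and kept only while use continues.

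- Exercise-first: the exercise change is E, unaffected. The peanut change runs from the third laboratory session to the fourth and equals P + (a − w)fE. The peanut-minus-exercise contrast shifts by +fE (peanut weeks only), −fE (washout only) or 0 (both).
- Peanut-first, if the device is held early: the peanut change is P + afE. The exercise change starts from a baseline raised by wfE and equals E − wfE. The contrast shifts by (a + w)fE, from 0 up to 2fE, toward peanuts.

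The documents give neither f nor the share choosing home exercise, and do not say whether a or w is ever 1. No bias can be computed. In the exercise-first sequence, where long possession is certain, use through all 8 weeks gives a shift of 0 under this model, so the 8-week figure measures exposure and not harm.

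**The case against.** The strongest reply is that the protocol already deals with off-schedule exercise. Stepping outside the exercise period would break the agreement on constant activity. Activity outside training and VO2max are measured at 4 time periods. For exercise-first participants the second and third sCPET bracket the washout, and the third and fourth bracket the peanut period. Participants are selected as sedentary, and unprompted interval training against an explicit agreement is speculative. Gym, stairs and running stay available whatever happens to the stepper. The study is a pilot.

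Most of this stands, and it limits the point to a preventable exposure. It does not remove it. The agreement is a promise. The Assessment Instruments table lists the Baecke questionnaire for initial status only and names no instrument for repeated activity measurement. Session-level heart-rate recording is described for training sessions and the run-in stretching, although the monitor is also listed for adherence. The consent pages are not available, so nothing can be concluded about further instructions given there.

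A reader might infer more than the documents support:

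- That exercise-first home users do train through the washout and peanut weeks. Nothing shows any use.
- That the comparison is tilted toward non-inferiority. The working shows that the shift can go either way or be nil in the exercise-first sequence.
- That peanut-first home users always hold the device for 8 weeks. The wording fixes only an earliest delivery date, and instruction on the exercise facility around the end of the washout is compatible with late delivery.
- That a number of affected completers, or a limit for detecting use by sCPET in one person, can be given. The home share and the test's error are not stated. VO2max would in any case serve as a check on group means, where it is more informative than in an individual.

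**Conclusion.** The point holds as a minor, cheap improvement. As written, the retrieval rule leaves exercise-first home users with the comparator's equipment for 8 of 12 weeks outside assigned exercise, and the delivery rule may give peanut-first home users up to 8 weeks of early possession. This rests on reading the two sentences literally and on the nominal 4 + 4 + 4 week schedule, and it applies only to those who choose home exercise. The size and sign of any resulting bias are unknown and it may be zero. The existing agreement and measurements guard against it in part.

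**What to change.** In the HIIT section, tie both dates to the participant's own exercise period:

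- **Retrieval:** at the end of that period. For exercise-first participants this is at about Laboratory Session 2 and sCPET 2, before the washout begins. For peanut-first participants the date does not change.
- **Delivery, peanut-first:** shipped to arrive near the end of the washout, in time for training to start directly after Laboratory Session 3.
- **Delivery, exercise-first:** leave it after the run-in. Delivery only after the baseline session would put carrier transit time between baseline and training, and could disturb the mid-luteal timing of women's tests.

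The number of shipments and pick-ups stays the same, but both must be scheduled by sequence, so the assignment must be known before dispatch. The narrative in Study Procedures places randomisation before Laboratory Session 1, while the run-in section lists it afterwards. The text should settle this, because only the former order allows dispatch by sequence ahead of the baseline. A short spell of early possession may remain, and it may be longer for women waiting for the right cycle phase. The change closes this one route only. Other off-protocol activity still rests on the agreement and the activity measurements.
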